16.4.3. Primary Endpoints Analysis

Clinical Adverse Events

AEs will be coded using the Medical Dictionary for Regulatory Activities. All treatment-emergent events will be included in the evaluation of safety. Treatment emergent includes any event that either occurs or worsens in severity after the onset of study treatment. Overall incidence of treatment-emergent events will be summarized; in addition, summaries by severity and by relationship to study treatment will be provided. The summary tables will include incidence estimates for the overall system organ class as well as for preferred terms within each system organ class. In order to assess whether the incidence of events changes over time, the incidence of key events may also be summarized by time period (e.g., 6-month time intervals).

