6.1.2. Secondary Objectives

Secondary objectives of this study in this study population are as follows:

- To describe MS-related outcomes, including MS relapse, disability progression, MS lesion formation, and patient-reported impact of MS, following long-term treatment with DAC HYP
- To assess the long-term immunogenicity of DAC HYP administered by PFS
- To assess the safety, tolerability, and efficacy of switching to DAC HYP in subjects previously on long-term treatment with interferon β -1a in Study 205MS301

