6.1.3. Exploratory Objective

6.2. Endpoints

6.2.1. Primary Endpoints

- Incidence of AEs and SAEs

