7. STUDY DESIGN

7.1. Study Overview

The design of Study 205MS303 is provided in [Figure 1](#). Approximately 1600 subjects will enroll in this study. This includes approximately 1200 subjects who completed Study 205MS301. Additionally, approximately 400 subjects from the other DAC HYP extension studies (205MS203 [SELECTED] and 203MS302 [OBSERVE]) will be eligible to enter Study 205MS303 at Week 144 of Study 205MS303 (Study 205MS301, Study 205MS203, and Study 205MS302 have been referred to as parent studies in the protocol).

All subjects will receive the same dose of DAC HYP as received in the parent studies; i.e., 150 mg by an SC injection every 4 weeks. The duration of DAC HYP treatment is up to approximately 5 years, or until availability of commercial product (whichever is sooner).

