7.2.2. Treatment

Subjects from Study 205MS301 continuing in Study 205MS303 will receive DAC HYP treatment for up to approximately 5 years, or until availability of commercial product (whichever is sooner), under this protocol. Subjects from Study 205MS203 and Study 205MS302 entering Study 205MS303 at Week 144 will have DAC HYP treatment for up to approximately 2 years, or until availability of commercial product (whichever is sooner), under this protocol.

CONFIDENTIAL

The information contained herein may not be used, disclosed, or published without the written consent of Biogen MA Inc.

At the Sponsor's discretion, 75-100 subjects from Study 205MS303 at selected sites may dose with DAC HYP using a single-use autoinjector that contains a PFS on 6 consecutive scheduled dosing days (Table 7).

Eligible subjects will have clinic visits scheduled every 4 weeks for up to Week 12 in this study, followed by clinic visits scheduled every 12 weeks.

Subjects who are dosing at home must be instructed to not administer their monthly dose of DAC HYP until the study site has contacted them to authorize dosing (after the *Study Neurologist* or their backup has reviewed LFT results obtained during the previous 32 days). Subjects need to record the date and time of dosing in their diary if they are dosing at home.

A window of ± 4 days applies to scheduled visits and home dosing.

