16.4. Safety and Efficacy

16.4.1. Analysis Population

Study 205MS303 Safety Population

The safety population will include all subjects who received at least 1 dose of DAC HYP in Study 205MS303. All safety analyses will be completed on the safety population.

Study 205MS303 Intent-to-Treat Population

The intent-to-treat (ITT) population will include all subjects who received at least 1 dose of DAC HYP in Study 205MS303. This population will be utilized for the efficacy analyses.

Study 205MS301 and Study 205MS303 Intent-to-Treat population

This population will include all subjects randomized to DAC HYP or Avonex in Study 205MS301 and received at least one dose of DAC HYP in Study 205MS303.

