16.4.2. General Methods of Analysis

Summary statistics will be presented. For continuous endpoints, summary statistics will generally include the number of subjects with data, mean, standard deviation, median, and range. Categorical endpoints will include the number of subjects with data and the percentage in each category.

Analyses will generally be descriptive in nature and will focus on data collected during Study 205MS303 only. However, for relevant efficacy analyses, the data may be summarized by previous treatment group (Avonex or DAC HYP). Also, statistical comparisons may be made between efficacy in Study 205MS301 and efficacy in Study 205MS303 among subjects previously randomized to Avonex in Study 205MS301.

All statistical tests will be 2-sided with an overall Type I error of 5%. Adjustments for multiple comparisons will not be considered.

CONFIDENTIAL

The information contained herein may not be used, disclosed, or published without the written consent of Biogen MA Inc.

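### The primary AE/SAE analysis is one pooled percentage with no time base, although planned treatment differs about 2.5-fold between cohorts, and no specified AE analysis addresses the safety of switching

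*Protocol*

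**What the plan says.** - The primary endpoint in Section 6.2.1 is "Incidence of AEs and SAEs", with no period attached.
- Section 16.4.3 gives its analysis: "Overall incidence of treatment-emergent events will be summarized; in addition, summaries by severity and by relationship to study treatment will be provided". Tables are by system organ class and preferred term. The same section adds that key events *may* also be summarized by period, for example 6-month intervals. The synopsis likewise makes a 3- or 6-month interval analysis optional.
- Section 16.4.1 defines one population for all safety analyses: "The safety population will include all subjects who received at least 1 dose of DAC HYP in Study 205MS303". Section 16.4.2 gives the general form of categorical summaries: "Categorical endpoints will include the number of subjects with data and the percentage in each category".
- On cohort sizes, Section 7.1 plans about 1600 subjects and says "This includes approximately 1200 subjects who completed Study 205MS301". About 400 more may come from Studies 205MS203 and 205MS302.
- On duration, Section 7.2.2 allows 205MS301 entrants up to about 5 years. For the rest, "Subjects from Study 205MS203 and Study 205MS302 entering Study 205MS303 at Week 144 will have DAC HYP treatment for up to approximately 2 years". Both limits give way to commercial availability if that comes sooner.
- A secondary objective in Section 6.1.2 is "To assess the safety, tolerability, and efficacy of switching to DAC HYP in subjects previously on long-term treatment with" interferon beta-1a in Study 205MS301. The split by previous treatment appears in Section 16.4.2: "for relevant efficacy analyses, the data may be summarized by previous treatment group (Avonex or DAC HYP".
- Section 16.4.4 takes the first DAC HYP dose as the baseline for laboratory values and vital signs. It shows vital-sign abnormalities, and optionally some laboratory summaries, by treatment group. That term is not defined in this single-arm study.

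**The concern.** The percentage of subjects with at least one event grows with time observed. When cohorts are observed for very different lengths of time, a pooled percentage reflects the cohort mix, dropout and local launch dates as well as the hazard.

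The cohorts also differ in kind. Former Avonex subjects start DAC HYP in this study. The others bring 96 to 144 weeks of exposure from Study 205MS301, or up to 144 weeks from Study 205MS203 on top of its predecessor studies. Exclusion criterion 1 removes anyone who permanently stopped treatment in a parent study, so the previously treated subjects have been selected for tolerating the drug and the switchers have not. An excess of events in the switchers' first year is the kind of finding the switching objective is meant to reveal. A pooled figure can dilute it.

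The protocol does allow for time elsewhere. Section 16.4.5 uses an annualized rate for relapses and Kaplan-Meier estimates for the proportions with relapse and with progression. The primary safety endpoint has no such provision.

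**Working it through.** The protocol states no expected AE rate, precision or power for the primary endpoint, so there is no such figure to reproduce. The planned total does add up: 1200 + 400 = 1600.

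**Time on one basis.** From the visit schedule, 240 weeks × 7 / 365.25 = 4.60 years (Week 0 to Week 240) and 96 weeks × 7 / 365.25 = 1.84 years (Week 144 to Week 240). The ratio is 240 / 96 = 2.5. Counting follow-up to 24 weeks after a last dose at Week 236, the figures are 260 weeks (4.98 years) and 116 weeks (2.22 years), a ratio of 2.2. With everyone followed to Week 240, person-years are 1200 × 4.60 ≈ 5520 and 400 × 1.84 ≈ 736. The later entrants are then 25% of subjects but 736 / 6255 = 11.8% of person-time.

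**Effect of follow-up alone.** Section 5.1 reports non-relapse SAEs in 15% of the DAC HYP group over a 96- to 144-week treatment period. Mean exposure is not given, so T is varied over that range. Assume a constant hazard h = −ln(1 − 0.15) / T, the same for everyone, with no dropout and full follow-up. The percentage with an event by time t is 1 − exp(−h·t), pooled with weights 0.75 and 0.25.

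| T | h per 100 patient-years | 240 weeks | 96 weeks | Pooled |
|---|---|---|---|---|
| 96 weeks | 8.83 | 33.4% | 15.0% | 28.8% |
| 120 weeks | 7.07 | 27.8% | 12.2% | 23.9% |
| 144 weeks | 5.89 | 23.7% | 10.3% | 20.4% |

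In each row the hazard is identical in the two cohorts, so follow-up time produces the whole gap. With all SAEs (24% in Section 5.1) the ranges are 36.7-49.6% and 16.7-24.0%, pooled 31.7-43.2%.

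**Effect of dropout.** Take T = 120 weeks and assume annual dropout d, with c = −ln(1 − d). The percentage observed with an event is h/(h + c) × [1 − exp(−(h + c)t)], and mean time at risk is [1 − exp(−(h + c)t)]/(h + c). Their ratio is h.

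| Annual dropout (assumed) | 240 weeks | 96 weeks | Pooled % | Rate per 100 patient-years |
|---|---|---|---|---|
| 0 | 27.8% | 12.2% | 23.9% | 7.07 |
| 10% | 22.3% | 11.1% | 19.5% | 7.07 |
| 20% | 17.8% | 10.0% | 15.9% | 7.07 |

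The rate is unchanged by construction, because the hazard is constant. The percentage falls by a third with no change in safety.

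**Dilution in switchers.** Study 205MS301 randomized 1:1, so assume 600 of the 1200 are former Avonex subjects. Keep T = 120 weeks and no dropout, and double their first-year hazard. Year-1 incidence is then 13.2% in switchers and 6.8% in the others. At Week 240 the switchers reach 32.7%. Pooled: (600 × 32.7% + 600 × 27.8% + 400 × 12.2%) / 1600 = 25.7%, against 23.9% without any excess. With 540 or 660 switchers the pooled figure is 25.5% or 25.9%.

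**The case against.** The strongest reply is that this is detail for the statistical analysis plan. Section 16.4.3 does not itself use the words crude or pooled; that reading comes from combining it with Sections 16.4.1 and 16.4.2. Nothing in the protocol rules out person-time rates or AE tables by previous treatment. This has some force, and it is why the point is not that such tables are forbidden. But the protocol does more than stay silent. It names a summary for its primary endpoint, ties the previous-treatment split to efficacy while setting a switching-safety objective, and chooses time-based estimators for relapse and progression.

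It is also fair to say that the protocol already contains partial remedies. The interval summary speaks to unequal follow-up, and Section 16.4.4 gives switchers their own laboratory and vital-sign baseline plus some displays by treatment group, which may mean previous treatment. A reader might infer that safety is never split at all; that is not supported. What remains is that the interval summary is optional and restricted to key events, and that none of these displays is an AE table tied to previous treatment.

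A third objection is that the illustration assumes one constant hazard although new starters and long-term users probably differ, and that exposure-adjusted rates lean on the same assumption. This stands as a limit. The percentages isolate the effect of follow-up and are not forecasts, and the rates need an interval table beside them.

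**Conclusion.** The point holds as a recommendation to improve the analysis. The committed primary summary has no time base, although planned treatment differs 2.5-fold (4.60 and 1.84 years). At one identical hazard the illustrative non-relapse SAE percentage is 23.7-33.4% in one cohort and 10.3-15.0% in the other, and the pooled 20.4-28.8% describes neither. A doubled first-year hazard in 600 switchers would move the pooled figure by only 1.8 percentage points (23.9% to 25.7%). These figures rest on an assumed constant hazard, an assumed exposure of 96 to 144 weeks behind the 15%, full follow-up and no dropout except where varied, and an assumed number of switchers.

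Three stronger readings go beyond the text. One is that the percentage estimates nothing definable: it is a valid description of subjects with an event during observed follow-up, but not a risk over a fixed period. Another is that the study cannot answer the switching question: the data will be collected, and the gap is that no AE analysis is specified for it. The third is a contrast of under 2 against nearly 5 years, which sets treatment time against treatment plus follow-up.

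**What to change.** In Section 16.4.3:

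- Keep the crude percentages and report beside them exposure-adjusted incidence: subjects with a first event per 100 patient-years at risk, with 95% CI, for AEs, SAEs, and hepatic and cutaneous events.
- Show these in columns for 205MS301 former Avonex, 205MS301 former DAC HYP, and 205MS203/205MS302 entrants.
- Change the interval summary of key events from *may* to *will*, with the subjects at risk in each interval as the denominator.

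The cost is a few more tables and columns from data already collected, with no change to study conduct. The drawback is that a single rate assumes a roughly constant hazard; the interval table checks that.

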16.4.4. Other Safety Endpoint Analyses

Unless otherwise specified, the baseline measurement for safety assessments such as laboratory values and vital signs was the measurement acquired on the day of the first receipt of DAC HYP. The first receipt of dosing of DAC HYP could be either Study 205MS303 (for subjects who received Avonex in Study 205MS301) or the parent studies (i.e., Study 205MS301, Study 205MS203, or Study 205MS302) for all other subjects.

Laboratory Data

Changes in laboratory values will be summarized using shift tables. Shift tables will include hematology, LFTs, kidney function tests, electrolytes, and other blood chemistry tests. Shifts will be presented from baseline of DAC HYP treatment (the last measurement acquired before or on the day of the first receipt of DAC HYP, e.g., Study 205MS303 baseline for subjects randomized to Avonex in Study 205MS301 and Study 205MS301 baseline for subjects randomized to DAC HYP 150 mg in Study 205MS301). Summaries of worst post-baseline laboratory values by clinically relevant categories may also be presented for selected parameters of interest by treatment group. For example, for LFT (alkaline phosphatase, ALT, AST, GGT, and total bilirubin), categories may be defined based on cutoff values relative to the ULN.

Vital Signs

Vital signs collected will be examined to determine the incidence of clinically relevant abnormalities. These abnormalities are described in [Table 9](#). For the purpose of the shifts from baseline, the baseline evaluation at the start of DAC HYP treatment will be used.

For each vital sign, the number of subjects evaluated and the number and percentage of subjects with the defined abnormality at any time post dosing will be presented by treatment group.

CONFIDENTIAL

The information contained herein may not be used, disclosed, or published without the written consent of Biogen MA Inc.

Table 9: Criteria to Determine Clinically Relevant Abnormalities in Vital Signs

Vital Sign	Criteria for Abnormalities
Temperature	>38°C or an increase from baseline of $\geq 1^\circ\text{C}$
Pulse	>120 beats per minute (bpm) or an increase from baseline of 20 bpm <50 bpm or a decrease from baseline of >20 bpm
Systolic Blood Pressure	>180 mmHg or an increase from baseline of >40 mmHg <90 mmHg or a decrease from baseline of >30 mmHg
Diastolic Blood Pressure	>105 mmHg or an increase from baseline of >30 mmHg <50 mmHg or a decrease from baseline of >20 mmHg

Physical Examination

The physical examination findings will be summarized.

16.4.5. Efficacy Endpoints Analyses

Annualized Relapse Rate

Relapses will be summarized over the follow-up period in Study 205MS303. For subjects in Study 205MS301 and Study 205MS303 ITT population, relapses may be summarized over the combined study period (Studies 205MS301 and 205MS303).

A negative binomial regression model will be used to estimate the adjusted ARR.

Proportion of Subjects with a Relapse

The proportion of subjects relapsed will be estimated using a Kaplan-Meier curve.

Disability Progression

Sustained disability progression is defined as at least a 1.0 point increase on the EDSS from baseline EDSS ≥ 1.0 that is sustained for 24 weeks, or at least a 1.5 point increase on the EDSS from baseline EDSS < 1.0 that is sustained for 24 weeks. The proportion of subjects with progression will be summarized using a Kaplan-Meier curve. In addition, summary statistics for EDSS and for the change from baseline in EDSS will be presented by visit, and for subjects who participated in Study 205MS301, by previous treatment group.

MSFC

Changes in the MSFC z-score will be summarized by study visit, and for subjects who participated in Study 205MS301, by previous treatment group. For subjects in Study 205MS301 and Study 205MS303 ITT population, MSFC z-score may be summarized over the combined study period (Studies 205MS301 and 205MS303). Details on the calculations of the z-score for each component will be described in the statistical analysis plan.

SDMT

Changes in the SDMT scores will be summarized by study visit and by previous treatment group in Study 205MS301. Change in the SDMT scores over the combined study period (Studies 205MS301 and 205MS303) will be calculated using the Study 205MS301 baseline visit

CONFIDENTIAL

The information contained herein may not be used, disclosed, or published without the written consent of Biogen MA Inc.

as baseline. Change in the SDMT score over the Study 205MS303 study period will be calculated using the last SDMT measurement in Study 205MS301 as baseline.

PASAT 3

Changes in the PASAT 3 scores will be summarized by study visit and by previous treatment group in Study 205MS301. Change in the PASAT 3 scores over the combined study period (Studies 205MS301 and 205MS303) will be calculated using the Study 205MS301 baseline visit as baseline. Change in the PASAT 3 score over the Study 205MS303 study period will be calculated using the Week 0/baseline visit as baseline.

MRI Endpoints

MRI endpoints will be summarized with descriptive statistics both as a continuous variable and categorically. Over time summaries and summaries by previous treatment group (Avonex or DAC HYP 150 mg) may also be provided. A negative binomial regression model will be used for the analysis of new or newly enlarging T2 lesions. The change in volume of lesions will be analyzed using an analysis of covariance.

Quality of Life Outcomes

Actual scores and change from baseline in quality of life endpoints will be summarized by visit.

Pharmacokinetics

The population for DAC HYP concentration analyses will include all subjects who received at least 1 dose of study medication and who have at least 1 sample available for analysis.

Serum concentration levels will be summarized with descriptive statistics by visit.

Antigenicity/Immunogenicity Data

Immunogenicity (i.e., ADAs to DAC HYP) will be assessed on subjects. Positive samples will be further tested for NABs to DAC HYP using a specific NAb assay. Results will be tabulated by time period and overall.

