Analyses will generally be descriptive in nature and will focus on data collected during Study 205MS303 only. Efficacy endpoints will be summarized for all subjects using descriptive statistics. For relevant efficacy analyses, the data may be summarized for subjects by previous treatment group (Avonex[®] or DAC HYP 150 mg). The adjusted ARR and number of new or newly enlarging T2 lesions will be estimated using a negative binomial regression model. The proportion of subjects with sustained progression and the proportion with a relapse will be estimated from the Kaplan-Meier curve. The incidence of AEs and changes in clinical laboratory assessments will also be summarized. An analysis by 3- or 6-month intervals may also be performed. Summary statistics for other safety, efficacy, and pharmacokinetic (PK) endpoints will be presented.

Sample Size Determination:

There is no formal sample size calculation for this study. The number of subjects in this study is determined by the number of subjects who completed Study 205MS301, Study 205MS203, or Study 205MS302, and enrolled in Study 205MS303.

Study Stopping Rules:

Biogen may terminate this study, after informing Investigators, at any time. Investigators will be notified by Biogen or designee if the study is placed on hold, completed, or closed.

CONFIDENTIAL

The information contained herein may not be used, disclosed, or published without the written consent of Biogen MA Inc.

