7.2.1. Baseline/Entry Visit Assessments

Subjects Entering From Study 205MS301

Tests/assessments performed at the subject's last visit in Study 205MS301 and within 28 days of the subject's first dose of DAC HYP (Week 0) in Study 205MS303 may be used as the baseline for Study 205MS303; if final Study 205MS301 tests/assessments are not performed within the 28-day window, they must be repeated upon entry into Study 205MS303 and before the first dose of DAC HYP is administered.

Subjects Entering From Study 205MS203 or Study 205MS302

The Week 144 Visit of Study 205MS303 will be the Entry Visit for subjects enrolled from Study 205MS203 or Study 205MS302. Any test/assessment done at the subject's last visit in parent studies and within 28 days of the subject's first dose in Study 205MS303 will be used as the baseline and does not need to be repeated at entry into Study 205MS303; tests/assessments performed >28 days before the Entry Visit must be repeated at the Entry Visit. Central LFT testing is *mandatory* at the Entry Visit.

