8. SELECTION OF SUBJECTS

8.1. Inclusion Criteria

To be eligible to participate in this study, candidates must meet the following eligibility criteria at the 205MS303 Baseline/Entry Visit or at the timepoint specified in the individual eligibility criterion listed (Note: Week 0/Day 1 is the Baseline Visit in Study 205MS303 for 205MS301 subjects. Week 144 is the Entry Visit in Study 205MS303 for 205MS203 and 205MS302 subjects):

1. Ability to understand the purpose and risks of the study and provide signed and dated informed consent and authorization to use protected health information (PHI) in accordance with national and local subject privacy regulations.
2. Must be a subject currently participating in Study 205MS301 who has completed either the Week 144 Visit or the End of Study Visit (Week 96) of Study 205MS301 OR subject currently participating in Study 205MS203 or Study 205MS302.
3. Women of childbearing potential must practice effective contraception during the study and be willing and able to continue contraception for 4 months after their last dose of study treatment.

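### After Week 144, by-visit change in EDSS and EQ-5D/EQ-VAS pools subjects whose time since baseline differs by 144 weeks

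*Protocol*

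**What the plan says.** **What is summarised.** On disability, Section 16.4.5 states: "summary statistics for EDSS and for the change from baseline in EDSS will be presented by visit". For subjects from 205MS301 it adds a split by previous treatment group. Under Quality of Life Outcomes it states: "Actual scores and change from baseline in quality of life endpoints will be summarized by visit". No split is attached to that sentence.

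**Who is included.** The Synopsis (Statistical Methods) says: "Efficacy endpoints will be summarized for all subjects using descriptive statistics". Section 16.4.1 defines the efficacy population: "The intent-to-treat (ITT) population will include all subjects who received at least 1 dose of DAC HYP in Study 205MS303". Parent study plays no part in that definition.

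**Where baseline lies.** Section 8.1 notes: "Week 0/Day 1 is the Baseline Visit in Study 205MS303 for 205MS301 subjects". Section 7.2.1 says: "The Week 144 Visit of Study 205MS303 will be the Entry Visit for subjects enrolled from Study 205MS203 or Study 205MS302". For these entrants, an assessment from the last parent-study visit that falls within 28 days of the first 205MS303 dose "will be used as the baseline and does not need to be repeated at entry into Study 205MS303"; otherwise it is repeated at entry. Table 3 schedules EDSS, EQ-5D and EQ-VAS at that entry visit.

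**Which labels apply afterwards.** Table 4 puts subjects from all three parent studies on one schedule, Week 156 to Week 240. EDSS falls at Weeks 168, 192, 216 and 240, and EQ-5D/EQ-VAS at Weeks 192 and 240.

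**The concern.** A visit label normally tells the reader how long ago baseline was. After Week 144 it no longer does so in this study. Under the same label, a subject from 205MS301 has 144 more weeks of change behind them than an entrant from 205MS203 or 205MS302. The protocol neither re-indexes the entrants' visits nor asks for by-visit change tables by parent study.

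If scores drift over time, adding subjects who restart at zero change pulls the pooled mean towards no change from the point where they join. With worsening EDSS, that could be read as stabilisation on long-term treatment. The first secondary objective (Section 6.1.2) is to describe MS outcomes, including disability, under long-term treatment, and a single-arm study has no concurrent control that would expose the artefact.

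**Working it through.** **Inputs from the Protocol**
- Baseline label: Week 0 for 205MS301 subjects (Section 8.1); Week 144 for 205MS203/205MS302 entrants (Section 7.2.1).
- Last on-treatment visit label: Week 240 for all (Table 4).
- Planned numbers: about 1200 from 205MS301 and about 400 entrants, about 1600 in total (Section 7.1).

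**Reproducing the plan's own durations.** The schedule counts 48-week years (Week 48 starts Year 2, Week 144 starts Year 4, Week 192 starts Year 5).
- 205MS301 subjects: 240 / 48 = 5 years.
- Entrants: (240 − 144) / 48 = 96 / 48 = 2 years.

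These match the approximately 5 and approximately 2 years in Section 7.2.2, so the 240-week and 96-week figures are the plan's own.

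**Pooled time since baseline.** Let w be the entrants' share of subjects with data at nominal week W. The pooled mean time since baseline is

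(1 − w) × W + w × (W − 144) = W − 144w.

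With equal retention, w = 400 / 1600 = 0.25 and 144w = 36 weeks.

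| Nominal week | 205MS301 | Entrants | Pooled mean | Shortfall (36 / W) |
|---|---|---|---|---|
| 168 | 168 | 24 | 132 | 21% |
| 192 | 192 | 48 | 156 | 19% |
| 216 | 216 | 72 | 180 | 17% |
| 240 | 240 | 96 | 204 | 15% |

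If every subject drifts by the same amount d per week, the pooled mean change at week W is (W − 144w) × d, against W × d for 205MS301 subjects. The percentage shortfall is then the last column, whatever the non-zero value of d.

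**Range over retention.** The Protocol gives only planned numbers, so the mixes below are assumptions about who is still in the study.
- 1200:200 (w = 0.143): 147.4 weeks at Week 168 (−12%); 219.4 at Week 240 (−9%).
- 900:400 (w = 0.308): 123.7 (−26%); 195.7 (−18%).
- 600:400 (w = 0.40): 110.4 (−34%); 182.4 (−24%).

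**The step where entrants join.** Take the Week 144 row as 205MS301 subjects only, at 144 weeks. At the planned mix, the next EDSS row (nominal Week 168) averages 132 weeks, so the time axis moves backwards by 12 weeks. This happens whenever 168 − 144w < 144, that is, w > 24 / 144 = 1/6. Below that share the curve flattens rather than reverses.

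**Scope check**
- SDMT and PASAT 3 are collected in 205MS301 subjects only (Section 12.1, Table 4).
- MSFC and MSIS-29 are last scheduled at Week 48 (Table 1), before any entrant joins.
- The Kaplan-Meier and relapse-rate analyses are not summaries of change by nominal visit.
- MRI is outside this point: Table 3 schedules no scan at entry.

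**The case against.** The strongest reply is that this belongs to the SAP. No single sentence orders a pooled column keyed to the schedule label; pooling follows only from reading the population definition, the Synopsis and the by-visit wording together. Analysis-visit derivation and table columns are usual SAP material, and an SAP could cure the problem. This stands in part. However, the protocol does more than leave a detail open: it fixes a by-visit display, an all-dosed population and a common label set that do not fit together. Section 16.4.5 also already sets endpoint-specific baselines for SDMT and PASAT 3, so detail of this kind is within its reach. An SAP that follows the text literally reproduces the mixture.

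The second reply is that a clean series is already required. EDSS change for 205MS301 subjects by previous treatment group contains no entrants and runs from Week 0 to Week 240. Section 16.4.2 also has the number of subjects with data shown, so the jump at entry would be visible. This stands for EDSS and lowers the weight of the point. For EQ-5D/EQ-VAS the split by previous treatment is only optional (Section 16.4.2).

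The third reply is that Section 16.4.5 does not name the EDSS baseline. The 96 weeks rests on Sections 7.2.1, 9.1 and 14.1. Section 16.4.4 uses first receipt of DAC HYP as baseline, but for safety assessments. If that were applied to EDSS, the 96-week figure would change, but times since baseline under one label would still differ.

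A reader might also infer that health resource utilisation and productivity (HRU, HRPQ) are affected. The documents do not support that: Section 6.2.2 lists them apart from quality of life, and no passage plans by-visit change summaries for them. Nor does the Week 168 figure apply to EQ-5D/EQ-VAS, which Table 4 collects only at Weeks 192 and 240.

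**Conclusion.** The point holds for EDSS at Weeks 168, 192, 216 and 240 and for EQ-5D/EQ-VAS at Weeks 192 and 240. As written, a pooled Week 240 change combines 240-week and 96-week changes; that gap is exact from the schedule. The pooled mean times of 132 and 204 weeks need the planned 1200:400 mix and equal retention. The 21% and 15% understatement further needs one common, non-zero linear drift across Avonex switchers, continuing DAC HYP subjects and entrants. The documents give no drift figure, and with no drift the bias vanishes.

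A reader might infer that the study's long-term efficacy results as a whole are biased by these percentages. They are not: the 205MS301-only tables by previous treatment group, the Kaplan-Meier and relapse-rate analyses, SDMT, PASAT 3, MSFC and MSIS-29 are untouched. The affected rows are descriptive, concern secondary endpoints and carry no test, so no error rate changes. The risk is a misread long-term course. Severity: moderate.

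**What to change.** In Section 16.4.5, under Disability Progression and Quality of Life Outcomes, state that change-from-baseline summaries after Week 144 are presented separately for 205MS301 subjects and for 205MS203/205MS302 entrants. Index the entrants by weeks since their own 205MS303 baseline, so that nominal Week 144 is their analysis Week 0 and nominal Week 240 their analysis Week 96. Any pooled row should use time since own baseline, not nominal week; a pooled row need not be ruled out. Naming the EDSS and EQ-5D/EQ-VAS baseline in the same sentences would close the remaining ambiguity.

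The cost is one derived analysis-visit variable and one extra table column. No data collection changes.
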